2.6.2 Statistical hypothesis, model, and method of analysis

The secondary (efficacy) variables during the study, listed in Table 2-7, will be summarized.

All analyses for the secondary (efficacy) endpoints will be performed descriptively. No statistical hypothesis is set for the secondary (efficacy) endpoints in this study.

For all efficacy analyses, the FAS will be used.

2.6.3 Handling of intercurrent events

Participants who discontinue from study treatment early due to any reason will be encouraged to stay in the study following the procedures. Every effort will be made to continue to follow participants who discontinued from study treatment up to Week 12. These are considered as RDO participants. If no RDO data was collected after study treatment permanent discontinuation, missing data will be handled without imputation and all available data will be used for the analysis.

| Novartis | Confidential | Page 38 of 54 |
|----------|--------------|------------------------|
| SAP | | Study No. CLOU064A1301 |

The analysis will account for different intercurrent events as explained in the following:

- Discontinuation of study treatment prior to Week 12 due to any reason: ignore, i.e., data collection will be maintained and available measurements post-treatment discontinuation will be used as if they had been obtained under the treatment: RDO data collected after study treatment discontinuation will be used for analysis (Treatment policy strategy).
- Treatment non-compliance (interruption), switch of background medication, or intake of rescue medication as per protocol prior to Week 12: ignore, i.e., data collected after these events will be used for analysis (Treatment policy strategy).
- Intake of strongly confounding prohibited medication (e.g., biologics treatment at any time before Week 12 (as identified by PD M-COMD03), cyclosporine after Week 8 to Week 12 (as identified by PD M-COMD04), systemic corticosteroids after Week 8 to Week 12 (as identified by PD M-COMD04)): measurements after this event will be excluded from the analysis and will be imputed using the worst value of the endpoint (e.g., 42 for UAS7 score at Week 12, 21 for ISS7 or HSS7 score) (Composite strategy (irrespective of potential occurrence of other intercurrent events)). Note: for the endpoint of UAS7 ≤6 at Week 2, intake of cyclosporine or systemic corticosteroids will not be considered.
- Intake of other prohibited medication prior to Week 12: ignore, i.e., Data collected after these events will be used for analysis (Treatment policy strategy).

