## 2.2 Secondary estimands

## Secondary estimand on efficacy as secondary endpoint: change from baseline in UAS7 score at Week 12

The secondary clinical question of interest regarding efficacy as secondary endpoint, change from baseline in UAS7 score at Week 12 is: What is the effect of remibrutinib treatment on the change from baseline in UAS7 score after 12 weeks of treatment in adult participants with CSU who are inadequately controlled by H1-antihistamine and receiving a stable locally label approved dose of a second generation H1-antihistamine, regardless of treatment discontinuation for any reason or intake of a different second generation H1-antihistamine as rescue medication and considering strongly confounding prohibited medication use as an unfavorable outcome? (see Section 12.5)

\* Assessment of confounder BCRP will be specified in the statistical analysis plan (SAP).

The secondary estimand on efficacy as secondary endpoint, change from baseline in UAS7 score at Week 12 is described by the following attributes:

- 1. **Population:** participants with inadequately controlled CSU despite treatment with second generation H1-antihistamine treatment who have CSU duration >6 months, a UAS7 score  $\geq$ 16, ISS7 score  $\geq$ 6 and HSS7 score  $\geq$ 6 in the last 7 days prior to start of treatment.
- 2. **Endpoint:** change in UAS7 from baseline at Week 12.
- 3. **Treatment of interest:** the study treatment (remibrutinib 25 mg b.i.d.) regardless of treatment compliance, with background medication of local approved second generation H1-antihistamine, and a different second generation H1-antihistamine as rescue medication.
- 4. **Summary Measurement:** the mean change from baseline.
- 5. Handling of remaining intercurrent events:
  - Discontinuation of study treatment due to any reason, treatment non-compliance (interruption), intake of rescue medication, or switch of background medication: Treatment policy strategy
  - Intake of strongly confounding prohibited medication (e.g., biologics treatment at any time before Week 12, cyclosporine after Week 8, systemic corticosteroids after Week 8): Composite strategy (irrespective of potential occurrence of other intercurrent events)
  - Intake of other prohibited medication: Treatment policy strategy

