### 6.2.2 Prohibited medication

Use of the treatments displayed in the below table are not allowed during the specified time period.

Table 6-2 Prohibited Medication

Medication	Prohibition period	Action taken
Biologics for treatment of CSU (including omalizumab and ligelizumab)	4 months prior to the first administration of study treatment until end of treatment 	Discontinue biologic treatment and closely monitor for potential associated adverse events.
Routine (more than 3 doses over 5-day period) oral corticosteroids	30 days prior to screening until end of treatment  Oral corticosteroids are only allowed as an additional rescue therapy for CSU AFTER Week  12, on an as-needed basis for unbearable symptoms as per Section 6.2.4. Other preparations of corticosteroids with limited systemic exposure for non-CSU indications (e.g., intra-nasal or any	Discontinue routine corticosteroids if medically justifiable and closely monitor for potential associated adverse events. If discontinuation of routine corticosteroids is not possible, discontinue study treatment.

Medication	Prohibition period	Action taken
	topical corticosteroids) can be used on an as-needed basis.	
i.v./IM/IA corticosteroids	30 days prior to screening until end of treatment  .	Discontinue i.v./IM/IA corticosteroids if medically justifiable and closely monitor for potential associated adverse events. If discontinuation of i.v./IM/IA corticosteroids is not possible, discontinue study treatment.
Leukotriene antagonists (including montelukast and zafirlukast)	From screening until end of treatment 	Discontinue Leukotriene antagonists and closely monitor for potential associated adverse events.
H2-antihistamines	From screening until end of treatment 	Discontinue H2-antihistamines and closely monitor for potential associated adverse events.
First-generation antihistamines	From screening until end of treatment 	Discontinue first-generation antihistamines and closely monitor for potential associated adverse events.
Second generation antihistamines other than the participant's defined background medication and rescue medication	From 7 days prior to the first administration of study treatment until end of treatment 	Discontinue all second-generation H1-antihistamines but the defined background and rescue medication and closely monitor for potential associated adverse events.

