Other immunosuppressive/immunomodulating medication with or without known effect on CSU including but not limited to hydroxychloroquine, methotrexate, cyclosporine A, cyclophosphamide, tacrolimus and mycophenolate mofetil	30 days or 5 half-lives (whichever is longer) prior to screening until end of treatment 	Discontinue immunosuppressive/ immunomodulating medication if medically justifiable and closely monitor for potential associated adverse events. If discontinuation not possible, discontinue study treatment.
Intravenous (i.v.) immunoglobulins or plasmapheresis	30 days prior to screening until end of treatment 	Discontinue i.v. immunoglobulins or plasmapheresis if medically justifiable and closely monitor for potential associated adverse events. If discontinuation not possible, discontinue study treatment.
Ultraviolet (UV) therapy	From screening until end of treatment 	Discontinue UV therapy and closely monitor for potential associated adverse events.
Any other therapy intended for the treatment of urticaria including but not limited to herbal therapies	From 2 weeks prior to the first administration of study treatment until end of treatment 	Discontinue any therapy intended for the treatment of urticaria and closely monitor for potential associated adverse events.
Live attenuated vaccines	6 weeks prior to baseline until at least 4 weeks after last dose of study treatment	Discontinue study treatment.
Strong inhibitors of CYP3A4	From 2 weeks prior to the first administration of study treatment until end of treatment 	Discontinue CYP3A4 inhibitor if medically justifiable and closely monitor for potential associated adverse events. If discontinuation

Medication	Prohibition period	Action taken
		not possible, discontinue study treatment
Moderate and strong inducers of CYP3A4	From 2 weeks prior to the first administration of study treatment until end of treatment 	Discontinue CYP3A4 inducers if medically justifiable and closely monitor for potential associated adverse events. If discontinuation not possible, discontinue study treatment.
Anticoagulant medication (e.g., warfarin, or NOAC)	From screening until end of treatment 	Only if medically justifiable, discontinue anticoagulant medication and interrupt study medication until anticoagulant effects have ended. Otherwise discontinue study treatment. Closely monitor coagulation parameters and associated adverse events.

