		Clinical monitoring should focus or skin (bruising, petechiae) and mucosa (e.g., gastro-intestinal trac bleeding including gingival and rectal, or conjunctival bleeding). In case of a significant bleeding event, study treatment must be discontinued immediately.
Anti-platelet medication except for acetylsalicylic acid up to 100 mg/d or clopidogrel up to 75 mg/d. The use of dual anti-platelet therapy (e.g., acetylsalicylic acid + clopidogrel) is prohibited.	From screening until end of treatment 	Only if medically justifiable, discontinue anti-platelet medication and interrupt study medication unti anti-platelet effects have ended. Otherwise discontinue study treatment. Closely monitor coagulation parameters and associated adverse events. Clinical monitoring should focus on skin (bruising, petechiae) and mucosa (e.g., gastro-intestinal tract bleeding including gingival and rectal, or conjunctival bleeding). In case of a significant bleeding event, study treatment must be discontinued immediately.

<sup>1 The day when patient receives the last study treatment dose (i.e., on Week 52 or in case of early treatment discontinuation the day of last dose of study treatment).

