# All participants who discontinue from study treatment prematurely should complete the Early treatment discontinuation visit at the time of treatment discontinuation.

For participants who discontinue from study treatment prior to Week 12, where possible they should be requested to return for visits after the Early treatment discontinuation visit as per the Assessment Schedule (Table 8-1) up to and including the Week 12 timepoint. At the Week 12 timepoint the study discontinuation visit should be performed

If the participant declines to continue with assessments as per the visit schedule up to Week 12, then they should complete the safety follow-up visit after the Early treatment discontinuation visit.

Participants who discontinue from study treatment after Week 12 should complete the safety follow-up visit indicated in the Assessment Schedule (Table 8-1) whenever possible.

If the participant cannot or is unwilling to attend any visit(s), the site staff should maintain regular telephone contact with the participant, or with a person pre-designated by the participant. This telephone contact should preferably be done according to the study visit schedule.

After discontinuation from study treatment, at a minimum, in abbreviated visits, the following data should be collected at clinic visits or via telephone/email contact:

- New / concomitant treatments
- Adverse Events / Serious Adverse Events

The investigator must also contact the IRT to register the participant's discontinuation from study treatment.

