2.5.4 Handling of missing values not related to intercurrent event

No imputation will be done for missing data. All available data will be used for the analyses.

If unexpectedly high incidence of adverse events of special interest (AESI) is observed, i.e., if incidence of AESI is greater than the one reported in the final analysis of A2201E1 study +20%, then sensitivity analysis will be performed for the AESI.

The following sensitivity analysis maybe performed on AESI, to assess the causality between the occurrence of AESI and medications. The sensitivity analysis will be implemented with the same target population, on AESI variable and the summary measure as for the primary estimand, but using the different assumptions or handling of intercurrent events.

- Intake of strongly confounding prohibited medication (e.g., biologics treatment (as identified by PD M-COMD03 and/or M-COMD03B), cyclosporine (as identified by PD M-COMD04 and/or M-COMD04B), systemic corticosteroids (as identified by PD M-COMD02B and/or M-COMD04 and/or M-COMD05)) : only measurements prior to intake of these prohibited medications will be used for analysis (While on treatment strategy).
- Intake of medications affecting the evaluation of potential risks, including: (a) anticoagulant/anti-platelet medications (other than acetylsalicylic acid up to 100 mg/day or clopidogrel) (as identified by PD M-COMD07); (b) live attenuated vaccines (as identified by PD M-COMD07); (c) strong CYP3A4 inhibitors (as identified by PD M-COMD07); (d) moderate/strong CYP3A4 inducers (as identified by PD M-COMD07), (e) Oral BCRP substrates that may have increased exposure when co-administered with remibrutinib (defined as pitavastatin, rosuvastatin, sulfasalazine and ubrogepan) (as identified by the name of concomitant medications entered in CRFs): only measurements prior to intake of these medications will be used for analysis (While on treatment strategy).

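### The Week 12 composite can miss a biologic or cyclosporine taken after remibrutinib is stopped, because SAP 2.6.3 finds these drugs only through protocol-deviation codes

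*SAP*

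**What the plan says.** **Estimand.** Protocol 2.2 handles strongly confounding prohibited medication by a "Composite strategy (irrespective of potential occurrence of other intercurrent events"). Biologics count at any time before Week 12, and cyclosporine counts after Week 8. SAP 1.2.2 repeats this. Protocol 4.1 gives the reason: such drugs could strongly bias the efficacy readout.

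**Detection.** SAP 2.6.3 makes the event operational by deviation code: "biologics treatment at any time before Week 12 (as identified by PD M-COMD03") for biologics, and M-COMD04 for cyclosporine and systemic corticosteroids. The worst value (42 for UAS7, 21 for ISS7 or HSS7) then replaces later measurements. Protocol 12.5.1 describes the same composite without any deviation filter, and SAP section 4 reports no change from the protocol.

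**Prohibition period.** In Protocol Table 6-2, biologics for CSU are barred from "4 months prior to the first administration of study treatment until end of treatment", and cyclosporine from "30 days or 5 half-lives (whichever is longer) prior to screening until end of treatment". Footnote 1 defines that end point, "in case of early treatment discontinuation the day of last dose of study treatment".

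**After stopping.** Protocol 9.1.1 asks participants who stop before Week 12 to keep attending through Week 12 where possible. SAP 2.1.1.4 feeds their retrieved drop-out (RDO) diary data into the weekly scores up to Week 12. SAP 2.6.3 uses those data under treatment policy. The minimum data collected after discontinuation include "New / concomitant treatments".

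**The concern.** A protocol deviation presupposes a protocol rule that was broken. Once the last study dose has been taken, Table 6-2 no longer bars a biologic or cyclosporine, so a drug begun the next day gives no evident ground for raising M-COMD03 or M-COMD04. With no deviation recorded, the composite does not fire, and the treatment-policy rule for discontinuation takes over.

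The same biologic would then be scored in two ways. Taken alongside remibrutinib, it gives a UAS7 of 42. Taken after remibrutinib is stopped, it is scored on its own result. Discontinuation is itself one of the other intercurrent events in the estimand's list, so stopping treatment should not switch the composite off.

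At stake are UAS7, ISS7 and HSS7 change, UAS7≤6 and UAS7=0 at Week 12, and the two cumulative-weeks endpoints. DLQI 0-1 is less exposed: under the SAP 2.1.1.4 windows, an early-discontinuation visit between Day 30 and Day 85 maps to Week 12 and takes precedence over a later study-discontinuation visit, so the DLQI used may predate the switch. Because the composite assigns the worst possible score, treating a retained switcher as observed can never make remibrutinib look worse. No sensitivity analysis is planned for the efficacy estimands that would show the difference.

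**Working it through.** **1. Sample size.** Protocol 12.8 expects about 100 screened, 30% screen failure and 15% dropout. 100 × (1 − 0.30) = 70 treated; 70 × (1 − 0.15) = 59.5, about 60 completers. The plan's figures reproduce, and n=70 is used below.

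**2. One participant traced through the rules.** Suppose the last dose is at Week 6, a CSU biologic starts at Week 7, and the diary continues to Week 12.

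| Step | Source | Result |
|---|---|---|
| Is the biologic prohibited at Week 7? | Table 6-2, footnote 1 | No; the period ended with the last dose |
| Is a deviation due? | Follows from the step above, unless the code is defined more widely | No stated basis |
| Does the composite fire? | SAP 2.6.3 | Not if M-COMD03 is absent |
| Which Week 12 score is used? | SAP 2.1.1.4 and 2.6.3 | The observed RDO score |
| What does the estimand call for? | Protocol 2.2 | The worst value, 42 |

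The path for cyclosporine is the same, with intake after Week 8 and code M-COMD04.

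**3. Size per missed switcher.** For k missed switchers with observed Week 12 UAS7 of u, among n analysed:

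- Shift in mean UAS7 change = k × (42 − u)/n. With k=1 and n=70: u=0 gives 42/70 = 0.60; u=16 gives 26/70 = 0.37.
- Shift in response rate = k/n = 1/70 = 1.43 percentage points, only if the switcher meets the response threshold.
- With n=60 instead, the figures are 42/60 = 0.70, 26/60 = 0.43 and 1/60 = 1.67 percentage points.

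**4. How many could there be?** The documents give no stopping rate by Week 12 and no switch rate. As an assumption, apply the 15% dropout to treatment stopping: 70 × 0.15 = 10.5 over 52 weeks. By Week 12 this is 10.5 × 12/52 = 2.4 if spread evenly, or 70 × (1 − 0.85^(12/52)) = 2.6 at a constant hazard. These figures count everyone who stops, and only some would switch and stay in follow-up. A range of 0 to 3 covers zero at one end and slightly more than every expected stopper at the other.

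- Mean UAS7 change: 0 to 3 × 0.60 = 0 to 1.8 points.
- UAS7≤6 response: 0 to 3/70 = 0 to 4.3 percentage points.

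**The case against.** The strongest reply is that the code definitions cannot be seen. M-COMD03 might be programmed to cover any biologic up to Week 12, on or off treatment; the SAP attaches it directly to the any-time-before-Week-12 wording. This stands. A reader might infer that a switcher certainly *is* scored on the new drug. The documents support only that one *can* be, because nothing in them extends a code beyond the prohibition it presumably polices.

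A second reply is that the estimand itself speaks of *prohibited* medication, so any limit to on-treatment use sits in the protocol too. A reader might infer a plain SAP departure from the estimand; what the text shows is an ambiguity that the detection rule resolves in the wrong direction. Reading *prohibited* as on-treatment only would leave the override of other intercurrent events with no force for discontinuation.

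A third reply concerns steroids. SAP 2.6.3 lists one code, "systemic corticosteroids after Week 8 to Week 12 (as identified by PD M-COMD04"), while the AESI sensitivity analysis lists "systemic corticosteroids (as identified by PD M-COMD02B and/or M-COMD04 and/or M-COMD05"). It is tempting to read that as the same gap, but it is not. Protocol 6.2.4 bars corticosteroid use for CSU before Week 12 without reference to dosing, so a deviation would still be due. The longer code list belongs to an analysis of the whole study, where different steroid rules apply after Week 12.

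Lastly, the effect needs retained data: at least 4 diary days in the week. Diaries may stop at the early discontinuation visit (Protocol 8.3.1), in which case the score is missing rather than favourable. Zero or one case is quite plausible. The documents also do not say that people switch mainly for lack of efficacy, or that post-treatment switching is the main case the composite was built for.

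**Conclusion.** The point holds for biologics and cyclosporine. Read with Table 6-2, the stated detection rule lets a participant who stopped remibrutinib and responded to another drug count as a Week 12 success, against the estimand's intent. Confidence is high that the text leaves this gap and lower on how the codes are actually programmed; a sentence showing that they reach past the last dose would remove it.

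The size is 0.37 to 0.60 UAS7 points per missed switcher with Week 12 UAS7 of 0 to 16, and 1.4 percentage points per false responder, at n=70. The overall range of 0 to 1.8 points and 0 to 4.3 percentage points rests on an assumed 0 to 3 retained switchers. The primary safety endpoint is untouched, the affected endpoints are descriptive with no hypothesis, and no decision rule changes. It is worth correcting because the correction is cheap and the error on retained switchers runs in one direction only.

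**What to change.** In SAP 2.6.3, replace the deviation codes for these two drug classes with identification from the concomitant-medication CRF, by drug name or ATC code, indication, and start and stop dates:

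- **Biologics for CSU:** any intake from Day 1 to the Week 12 assessment.
- **Cyclosporine:** any intake overlapping the period after Week 8 to Week 12, whatever its start date.

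Apply this whether or not study treatment has stopped and whether or not a deviation was raised. Add that *prohibited* in the composite names the drug class, not the on-treatment prohibition period. Indication is needed so that a biologic given for another disease is not scored as CSU failure. Stop dates are needed so that cyclosporine begun before Week 8 and continued past it is not missed.

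The data exist. Protocol 6.2.1 requires all medication after enrolment to be entered on the eCRF, Protocol 9.1.1 continues collection after discontinuation, and the SAP already identifies BCRP substrates by CRF medication name in its AESI sensitivity analysis. No clinical rule or data collection changes. The cost is SAP wording and a programmed drug list, and the results may come out slightly less favourable.

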2.6.4 Handling of missing values

See Section 2.6.1 for the derivation of the each variable.

If there is any intermittent missing data not due to any of the intercurrent events as we defined above, the missing data will be handled without imputation and all available data will be used for the analysis.

2.6.5 Sensitivity analyses

No sensitivity analysis is planned for the secondary (efficacy) estimands.

